Subjects will be reassured that participation is completely voluntary and does not affect their treatment, their relationship with their providers, or the university to minimize the possibility of coercion or undue influence. The patients will be asked that they understand the opportunity to participate and their complete freedom to decline. This will also be asked if they understand and if they have any questions. There is no minimum time period needed between informing the patient of the study and time of consent. Subject will all be encouraged to take as much time as they need.

This study will obtain HIPAA authorization prior to enrollment. HIPAA authorization is embedded within the study consent form, which will be reviewed with all participants by the physician obtaining consent. Specific information that will be obtained includes prior medical history, surgical history, reproductive health history including child bearing, drug allergies, age, and ethnicity. This information will obtained by health care providers, not research coordinators, as deemed necessary for a more complete and accurate medical history of the patient.

Page 18 of 23

Subjects not fluent in English

Given that the primary outcome is measurement with the PPQ questionnaire and it is only validated in English, non-English speaking patients will be excluded.

Cognitively Impaired Adults/Adults Unable to Consent/Use of a Legally Authorized Representative

Cognitively Impaired Adults will not be included in the study.

Subjects who are not yet adults (infants, children, teenagers)

All subjects will be 18 years of age or older. No infants, children or teenagers will be enrolled in the study.

25.Documentation of Consent

We plan to document consent, and the Consent form is attached. We do not plan on collecting/storing tissue samples. We will not obtain consent verbally. We will not be using a script, information sheet, or other mechanism.

26. Study Test Results/Incidental Findings

26.1. **Individual Results:** Patients will be randomized to watch either a physician-centered or patient-centered video. Therefore, the patients will be aware which study arm they are randomized to. Study results for individual participants will not be shared.

26.2. Incidental Findings:

We do not anticipate that the research being conducted will result in incidental findings. Every patient will receive the practice's standard of care regarding a pre-operative work up, which may include different laboratory tests and imaging studies, as determined by their other active medical issues. These results are not directly a part of the research being conducted, and will hence be disclosed to the patient. They will not, however, affect randomization.

27. Sharing Study Progress or Results with Subjects

The patients will be aware which arm of the study they are randomized to. Therefore, we will not require to provide subjects with a summary of the trial. We do not intend to seek out study participants to disseminate information once the study is complete. Women who are interested in the results will be provided the information where to read the manuscript once it is published. Study results for individual participants will not be shared.

28.Inclusion of Vulnerable Populations

There will not be any vulnerable populations included in this study. Those electing for surgery will not be coerced into doing so, nor will they be coerced into participating in this trial.

Page 19 of 23

29. Community-Based Participatory Research

There will be no involvement of the community in this research.

30.Research Involving American Indian/Native Populations

This research does not specifically target this population. If a Native American female is a candidate for this study she will be offered participation.

31.Transnational Research

This study is not transnational

32.Drugs or Devices

No drugs or devices will be utilized in this study.

Page 20 of 23

Version 5 Date: 9.25..2017

Checklist Section

This section contains checklists to provide information on a variety of topics that require special determinations by the IRB. Please complete all checklists relevant to your research.

I. Waivers or Alterations of Consent, Assent, and HIPAA Authorization

A. Partial Waiver of Consent for Screening/Recruitment

We are not requesting a partial waiver of consent

Partial Waiver of HIPAA Authorization for Screening/Recruitment

We will not be reviewing records to identify potential subjects

B. Waiver of Documentation of Consent

NA. We are not requesting a waver of documentation of consent. We do not intend to obtain consent verbally. We will be obtaining signatures from subjects on a consent form to document consent

C. Alteration of Consent

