Aim #1: To create two videos to be used to counsel patients who have elected to undergo a MUS procedure. One video will present the risks, benefits and alternatives to MUS surgery by a physician, mimicking traditional counseling prior to surgery. The second video will also explain the risks, benefits and alternatives to the MUS surgery utilizing a patient mentor who has undergone the MUS procedure will describe the patients' perception of the information. The patient-centered video will also include topics that have previously been identified by focus groups as important patient-centered aspects of pre-surgical counseling.

> Page 4 of 23 Version 5

Aim #2: To compare the impact of video counseling between women randomized to a physician-centered video and a patient-centered video. **Hypothesis:** Women randomized to a patient centered-video will report higher satisfaction and preparedness as measured by validated scales. They will have higher scores on the Post-operative preparedness questionnaire (PPQ), Preparedness Scale and the Surgical Decision Satisfaction (SDS-PFD) questionnaire; and lower scores on the Decision Regret Scale (DRS-PFD) questionnaire than women randomized to view the physician-centered video prior to undergoing midurethral sling surgery.

Aim #3: To compare a women's decisional conflict post-operatively in women randomized to the physician-centered video and the patient-centered video. **Hypothesis:** There is a reduction of decisional conflict in women randomized to the patient-centered video.

Aim #4: To determine if there are differences in anxiety scores in women who watch the patient-centered video versus the physician centered video. **Hypothesis:** Anxiety scores measured by the State Trait Anxiety Inventory (STAI: Y-6 Item) questionnaire are decreased by a pre-operative patient-centered counseling video.

2. Background

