Power Analysis: We will compare the percent of patients that feel completely prepared (strongly agree on the Patient Preparedness Questionnaire, a 1-6 Likert scale) between the two intervention groups, those randomized to a Physician-centered vs Patient-centered video. Firoozi et al. found 30% were "completely prepared" in the standard office counseling group. However, we expect a "floor effect" where a higher percentage of completely prepared at 40%. As there is high satisfaction in this population that will be undergoing mid-urethral sling surgery. A sample size of 24 patients per group would be adequate to detect a difference of 40% (Physician-centered video) versus 78% (Patient-centered video) in those being "completely prepared" with 80% power and an alpha of 0.05. This is a feasible power analysis since Firoozi et al found an improvement to 79% using the shared appointments. Therefore our recruitment goal will be to increase randomization to a total of 60 subjects, 30 patients per group, which will also allow for a 20% loss to follow up.

6. Study Timelines

Based on the current surgical volume in the UNM division of urogynecology, it will take 12 months to recruit the 43 patients; it would take 18 months to recruit~ 60 patients. Then, for data analysis and composition of the manuscript, we estimate that this will take 6 months.

Page 7 of 23

Timeline	Feb. 2017- May 2017	June 2017- Dec. 2018	Jan 2019-March 2019	April 2019- June 2019
Video Development	\longleftrightarrow			
Subject recruitment, surgery, through 6 week follow up				
Data analysis		•	*	
Manuscript preparation				\longleftrightarrow

7. Study Endpoints

First, the physician-centered and patient-centered video will be created. Once developed, the **primary endpoint** of our study is to determine if there is a difference in patient preparedness and satisfaction in those women undergoing a MUS procedure who have watched a patient-centered versus a physician-centered video watched at their pre-operative visit. Our **secondary endpoints** include differences in preparedness, satisfaction and decisional conflict scores. Our **exploratory endpoint** is to investigate differences in anxiety 6 weeks after corrective MUS surgery in those who undergo a pre-operative patient-centered video compared to a physician-centered video.

Given that a MUS surgery is routinely performed currently, we do not have any **safety endpoints**.

8. Research Setting

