- 1. First, two videos will be created to counsel patients who have decided to undergo a MUS procedure. One video, the physician-centered video, will be developed with well-described literature involving the risks, benefits, and alternatives to MUS. Physicians from the urogynecology division will be videotaped explaining these risks. The second video will be the patient-centered video. We will meet with the patient mentors who were a mentor in the Preliminary Study of Peer Support Groups and Pelvic Floor Disorders. We will create a script with the patient mentors that will include the risks, benefits, and alternatives in lay terms as well as topics that have previously been identified by focus groups as important patient-centered aspects of counseling. This will include aspects of quality of life factors such as catheterization and when patients can return back to work. Once we have created the script with the mentors who agree to be filmed; the mentors will be videotaped explaining these topics. All participants involved in the creation of the video will sign an informed consent prior to the development of the video. The participants will include the physicians counseling on the video and women acting as mentors on the video.
- 2. Once the videos are complete, we will perform a randomized clinical trial clinical trial to determine if a patient-centered versus a physician-centered video will increase preparedness and satisfaction. The target population is female subjects with stress urinary incontinence who are planning to have a MUS procedure. All subjects will be given written study consents during their clinic visit when they are scheduled for their MUS. After enrollment, subject's data collected include *Patient Demographics*: Age; self-reported race and ethnicity; body mass index (BMI); vaginal parity, education level, socio-economic status. Also, *Medical/Surgical History*: Medical comorbidities; prior POP surgeries or incontinence procedures, prior hysterectomy. They will also perform a health literacy assessment utilizing the validated REALM-SF questionnaire. They will also complete the PGI-I and STAI: Y6 questionnaire at the baseline clinic visit.

Page 10 of 23

Version 5 Date: 9.25..2017 Once this is performed, patients will return for their standard pre-operative clinic visit. Patients will then be randomized once they check-in to the waiting room.

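### Aim 3 promises a post-operative comparison of decisional conflict, but the DCS is given only before surgery; a lesser point is that the baseline STAI goes unused in the analysis of 6-week anxiety

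*Combined protocol and SAP*

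**What the plan says.** Aim 3 (Section 1) is "To compare a women's decisional conflict post-operatively in women randomized to the physician-centered video and the patient-centered video", with the hypothesis "There is a reduction of decisional conflict in women randomized to the patient-centered video". Section 7 lists the secondary endpoints as "differences in preparedness, satisfaction and decisional conflict scores" and gives no time point.

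Section 11 places the DCS in the set of questionnaires completed at the pre-operative visit, after the assigned video and the scripted counselling. Its list for the 6-week visit holds five instruments: SDS-PFD, DRS-PFD, STAI, UDI-6 and PGI-I. Table 1 has one mark in the DCS row, in the column for the time straight after the video.

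On anxiety, the Aim 4 hypothesis is "Anxiety scores measured by the State Trait Anxiety Inventory (STAI: Y-6 Item) questionnaire are decreased by a pre-operative patient-centered counseling video". Section 7 says the exploratory endpoint "is to investigate differences in anxiety 6 weeks after corrective MUS surgery". Section 11 states, of the enrolled women, "They will also complete the PGI-I and STAI: Y6 questionnaire at the baseline clinic visit". Section 12 gives a chi-squared test for the primary PPQ item and, for all other analyses, a two-way ANOVA with arm and questionnaire item as its factors.

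**The concern.** Decisional conflict is a secondary endpoint with an aim of its own, and the aim and the data collection point to different times. A report written to Aim 3 would either have no data or would present a pre-operative score as a post-operative one. The documents do not say which of the two is the mistake. If the schedule is wrong, the missing measurements cannot be recovered once women have passed their 6-week visit.

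The hypothesis adds a second ambiguity. It speaks of a reduction, yet no DCS is taken before the video, so only a difference between arms can be tested, not a change within women.

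The STAI point is smaller. The trial collects a baseline anxiety score but plans no analysis that uses it. An unadjusted comparison at 6 weeks is valid under randomisation. What is lost is precision on an exploratory endpoint.

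**Working it through.** **Decisional conflict.** No arithmetic applies beyond counting, so the places that could schedule the DCS are set side by side.

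| Place | Before the video | Pre-operative visit, after video | 6 weeks |
|---|---|---|---|
| Aim 3 | not mentioned | not mentioned | comparison described as post-operative, no visit named |
| Section 7 | no time given | no time given | no time given |
| Section 11, text | no | yes | no (0 of 5 instruments listed) |
| Table 1 | no | yes | no (0 of 4 instruments marked) |

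The four instruments marked at 6 weeks in Table 1 are the PPQ, DRS-PFD, SDS-PFD and UDI-6. Table 1 and the text disagree on other instruments: the table has no STAI or PGI-I row and marks the PPQ at 6 weeks. They agree on the DCS, so a badly extracted table does not explain the gap. The outcome-measure entry for the DCS describes its 16 items and scoring but gives no timing.

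The DRS-PFD at 6 weeks cannot stand in. Section 11 describes it as a measure of regret, and Aim 2 already claims it, expecting "lower scores on the Decision Regret Scale (DRS-PFD) questionnaire".

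Count per woman: DCS before the video 0, pre-operative after the video 1, post-operative 0.

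**Baseline STAI.** The documents give no sample size for the STAI or the DCS. The number available at 6 weeks follows from Section 5, which sets 30 women per arm, "which will also allow for a 20% loss to follow up":

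- 60 × (1 − 0.20) = 48, or 24 per arm. This agrees with the plan's own inflation, 24 / (1 − 0.20) = 30.

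Let r be the correlation between baseline and 6-week STAI totals. The documents do not give it, so 0.3, 0.5 and 0.7 are assumed. The other formulas are:

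- Variance under ANCOVA relative to the unadjusted 6-week comparison: 1 − r².
- Equivalent unadjusted sample per arm: 24 / (1 − r²), ignoring the one degree of freedom spent on the covariate.
- Detectable difference in SD units at 80% power, two-sided 0.05 (the plan does not state sidedness): (1.96 + 0.84) × √(2/24) = 0.81 unadjusted, multiplied by √(1 − r²) when adjusted.

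| Assumed r | 1 − r² | Variance reduction | Equivalent n per arm | Detectable difference (SD) |
|---|---|---|---|---|
| unadjusted | 1.00 | none | 24 | 0.81 |
| 0.3 | 0.91 | 9% | 26.4 | 0.77 |
| 0.5 | 0.75 | 25% | 32.0 | 0.70 |
| 0.7 | 0.51 | 49% | 47.1 | 0.58 |

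**The case against.** On Aim 3, the conflict comes down to one word. The schedule is clear in two places, the secondary endpoint carries no time point and so fits the scheduled DCS, and a report could simply give the score at the visit where it was taken. A drafting slip is plausible: Aim 2 expands PPQ as a post-operative questionnaire, while Section 11 calls it the Patient Preparedness Questionnaire and words its key item about surgery still to come. A 6-week DCS may also seem unnecessary when regret is already measured then.

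Most of this stands, and it limits the weight of the point: no scheduled comparison is invalid. It does not remove the contradiction. Plausible is not certain, nothing in the documents settles whether the aim or the schedule is wrong, and regret is a different construct assigned to a different aim.

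On the STAI, Section 12 names no STAI analysis at all, so non-use of the baseline score is inferred from the generic ANOVA. The Aim 4 wording could even be read as change from baseline. Baseline collection rests on the Section 11 text alone, since Table 1 has no STAI row. The correlations are not anchored in the documents. Section 24 describes a gap of days to months between the decision for surgery and the pre-operative visit, with surgery and six further weeks to follow, so nothing supports the top case in particular. All of this is fair. It makes the point a modest improvement rather than the correction of an error, but it does not argue against naming an analysis that uses the baseline score.

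**Conclusion.** The concern holds. Aim 3 cannot be answered as worded, because one pre-operative and no post-operative DCS will exist for each woman. This rests on the text and Table 1 agreeing, with no other section supplying a later DCS. It is a contradiction between an aim and its data on a secondary endpoint. The between-arm comparison that is scheduled is sound.

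The STAI point also holds, as a free improvement. The gain depends wholly on the assumed correlation: small at 0.3 (24 women per arm do the work of about 26), useful at 0.5 (about 32), large at 0.7 (about 47). These figures assume the full 20% loss by 6 weeks. The primary outcome and the sample size are untouched by either point.

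**What to change.** Decide which time point Aim 3 intends, then make one of two changes.

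- If the schedule is right, reword the aim: *To compare decisional conflict (DCS) between arms at the pre-operative visit, after video and counselling.* Reword the hypothesis as lower DCS scores in the patient-centered arm than in the physician-centered arm, which also removes the unmeasured reduction. Cost: wording only.
- If a post-operative comparison is intended, add the DCS to the 6-week questionnaires in both the Section 11 text and Table 1, and name 6 weeks as the time point in Aim 3. Cost: 16 more questions per woman at a visit that already takes place.

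For anxiety, add one sentence to Section 12: the 6-week STAI total is compared between arms by ANCOVA with the baseline STAI total as covariate. Cost: no new data, provided the baseline STAI is collected as the Section 11 text says. Adding an STAI row to Table 1 would make that explicit.

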Randomization: Randomization assignment will be generated by a computer based randomization table and assigned by a research coordinator not otherwise involved in the study. Assignments will be kept in sealed opaque envelopes numbered sequentially. As an adjunct to standard pre-operative counseling, the physician will call the research coordinator and the next envelope in the sequence will be opened randomizing the patient to the patient-centered or physician centered video

Once randomized, patients will view the video they are assigned to in the waiting room utilizing video viewing devices with headphones. Once the video is complete, patients will receive standard pre-operative counseling for the midurethral sling procedure by their provider. The pre-operative counseling will be scripted. They will then complete the PPQ, preparedness scale, SDS-PFD, DCS.

At the 6 week post-operative visit, they will fill out the questionnaires: SDS-PFD, DRS-PFD, and STAI: Y6, UDI-6, PGI-I will be completed (Table 1). The physician will also complete an adverse events form at that time.

	Baseline Clinic Visit	Immediately after consents and video	6 weeks postoperatively
PPQ		Χ	X
Preparedness Scale		X	
DCS		X	
DRS-PFD			X
SDS-PFD		X	X
UDI-6	X		X
Demographics	X		

Table 1: Outcomes collected at various time points

The primary outcome is preparedness for surgery with an adjunct patient-centered versus a physician-centered video at their pre-operative visit. After they watch the video in the waiting room, all patients will receive standard pre-operative counseling for the midurethral sling procedure by their provider. They will then fill out the preparedness questionnaires. Our secondary outcome is satisfaction, which will also be evaluated using the SDS-PFD at her pre-operative visit after consents and the video as well as their 6 week visit.

The midurethral sling will be performed by surgeons in the standard fashion.

Outcome Measures:

- 1. Patient Preparedness Questionnaire (PPQ): Assess the level of pre-operative preparedness according to each preparedness question. Measured by question 11 on the Patient Preparedness Questionnaire (PPQ): "Overall, I feel prepared for my upcoming surgery." The 11-question PPQ contains questions on both knowledge and preparedness for the planned surgical procedure. The PPQ has demonstrated construct validity properties in previous studies.

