A Midurethral Sling (MUS) surgery is the most common type of surgery to correct stress urinary incontinence. The sling is a narrow strap made of synthetic mesh that is placed under the urethra and acts as a hammock to lift or support the urethra.

There are no study related costs to the participants. Whether enrolled in the physician-centered video or the patient-centered arm of the study, participants will not be billed for the study materials. They have already chosen to undergo surgery, and they will receive prior authorization from their 3rd party payers, or they will have worked out financial assistance, if needed, with the hospital prior to their surgical date. These costs will be billed to their insurance provider and costs may range from copay only to full cost of treatment.

22. Compensation

For enrollment in the study, each patient will be compensated with a \$60 merchandise card. They will receive a \$20 merchandise card at their pre-operative evaluation and a \$40 merchandise card at their 6-8 week post-operative visit. The merchandise card is reasonable compensation for the inconvenience of participating in a research study due to the multiple questionnaires evaluating preparedness, satisfaction, knowledge, and anxiety after watching a physician or patient-centered video.

23. Compensation for Research-Related Injury

If participants are injured or become sick as a result of this study, UNMHSC will provide emergency treatment at the study participant's cost. No commitment is made by the University of New Mexico Health Sciences Center to provide free medical care or money for injuries to participants of the study. Reimbursement for treatment for all related costs of care will be sought from the participant insurer, managed care plan, or other benefits program. The participant will be responsible for any associated copayments or deductibles required by the insurance. Participants will be encouraged to

Page 17 of 23

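### With no STAI between the video and the operation, Aim 4's 6-week comparison is valid but cannot show whether the video lowers anxiety before surgery

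*Combined protocol and SAP*

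**What the plan says.** The objective of Aim 4 is "To determine if there are differences in anxiety scores in women who watch the patient-centered video versus the physician centered video". No time point is attached. The hypothesis under it is that "Anxiety scores measured by the State Trait Anxiety Inventory (STAI: Y-6 Item) questionnaire are decreased by a pre-operative patient-centered counseling video".

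Section 7 (Study Endpoints) makes anxiety the exploratory endpoint and supplies a time: the purpose "is to investigate differences in anxiety 6 weeks after corrective MUS surgery in those who undergo a pre-operative patient-centered video" compared with the physician-centered video.

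Section 11 (Study Procedures) sets the schedule:

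- Baseline: "They will also complete the PGI-I and STAI: Y6 questionnaire at the baseline clinic visit". Women then come back for the pre-operative visit, where they are randomized and watch the video.
- After video and scripted counseling: "They will then complete the PPQ, preparedness scale, SDS-PFD, DCS".
- After surgery: "At the 6 week post-operative visit, they will fill out the questionnaires: SDS-PFD, DRS-PFD, and STAI: Y6, UDI-6, PGI-I will be completed". This sentence cites Table 1, but Table 1 has no STAI row.

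Section 22 (Compensation) justifies payment by the burden of "multiple questionnaires evaluating preparedness, satisfaction, knowledge, and anxiety after watching a physician or patient-centered video".

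**The concern.** The video is offered as preparation for surgery, and the Background supports it with a video study that reported better preparedness and less anxiety. A reader of Aim 4 would expect at least one anxiety reading while the operation is still ahead. Preparedness, decisional conflict and satisfaction are all measured straight after the video and counseling, and satisfaction again at 6 weeks. Anxiety is not measured at that visit, and no reason is given.

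What is at stake is how the anxiety result will be read. If the arms look alike at 6 weeks, the report may say that the patient-centered video does not affect anxiety, although the period before surgery was never observed. A pre-operative reading that was not taken cannot be recovered later.

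**Working it through.** **1. Schedule.** Every mention of the STAI or of anxiety measurement, in time order:

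| Time | Video seen? | Surgery done? | STAI? | Source |
|---|---|---|---|---|
| Baseline clinic visit | No | No | Yes | Section 11 text |
| Pre-operative visit, after video and counseling | Yes | No | No | Section 11 text |
| 6 weeks post-operatively | Yes | Yes | Yes | Section 11 text; Section 7 |

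No reading falls in the only row where the video has been seen and surgery is still to come. Table 1 does not settle the matter, because it lists the STAI at no time.

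**2. What each contrast can show.**

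- *Between arms at 6 weeks.* Surgery, recovery and scripted counseling occur in both arms. Apart from chance and loss to follow-up, a difference is an effect of video assignment. Recovery and surgical result may carry or dilute that effect, but they do not confound it.
- *Within patient, baseline to 6 weeks.* The wait, the operation and the recovery all lie between the readings, so a fall cannot be credited to the video.
- *Between arms before surgery.* Not measured.

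**3. The plan's own sample size.** It is for the primary preparedness outcome only: 40% versus 78%, alpha 0.05 (two-sided assumed), 80% power, 24 per group. With pooled variance and p̄ = (0.40 + 0.78)/2 = 0.59:

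n = [1.960·√(2·0.59·0.41) + 0.842·√(0.40·0.60 + 0.78·0.22)]² / 0.38² = (1.363 + 0.540)² / 0.1444 ≈ 25.1, so 26 per arm.

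This is within two patients of the stated 24, which has 78.1% power by the same method. The inflation also reproduces: 24/(1 − 0.20) = 30. The documents give no STAI effect size or SD, so 24 to 30 per arm is the range used below.

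**4. What the 6-week STAI comparison can detect.** Smallest difference at 80% power, normal approximation: (1.960 + 0.842)·√(2/n).

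- n = 24: 0.81 SD. n = 30: 0.72 SD. (Exact t-test: 0.83 and 0.74.)
- Adjusting for baseline multiplies this by √(1 − r²). With an assumed baseline to 6-week correlation r of 0.3 to 0.7, n = 24 gives 0.77 to 0.58 SD and n = 30 gives 0.69 to 0.52 SD.

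**5. Illustration of dilution.** Two-sample t-test, two-sided 5%, noncentrality d·√(n/2). The 0.8 SD effect and the retained fractions are assumptions.

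| Effect when measured | n = 24 per arm | n = 30 per arm |
|---|---|---|
| 0.8 SD (after video) | 77.4% | 86.1% |
| 0.4 SD (half remains) | 27.4% | 33.2% |
| 0.2 SD (a quarter remains) | 10.4% | 11.9% |

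These are unadjusted. Baseline adjustment with r = 0.5 divides d by √0.75; the 0.4 SD row then becomes 34.7% and 42.1%.

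**The case against.** The strongest reply is that the plan is coherent as it stands. Aim 4 names no time, Section 7 supplies 6 weeks, the STAI is given at 6 weeks, and a baseline reading is available for adjustment. In the hypothesis, the word pre-operative describes the video and not the anxiety. The patient-centered script covers catheterization and return to work (Section 11), so an effect lasting past surgery is plausible. The endpoint is exploratory.

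Most of this stands, and it limits the point. A reader might infer that Aim 4 cannot be answered at all, or that a 6-week difference would be uninterpretable because recovery intervenes. The documents support neither: the aim is a randomized between-arm comparison, and Section 7 and the 6-week visit match.

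Two supporting readings should also be kept weak. Section 22 can be taken to promise a reading directly after the video, but the 6-week STAI is also after the video, and the payment covers that visit. Section 24 puts days to months between the decision for surgery and the pre-operative visit, but it does not mention the baseline questionnaires. It also places study consent at the pre-operative visit, whereas Section 11 places consent and baseline data earlier. The length of the gap from baseline to video is therefore uncertain.

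The reply does not remove the gap itself. Anxiety between video and surgery is not observed, and nothing in the plan warns the reader that the 6-week result is silent on it.

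**Conclusion.** The point holds in a limited form. The schedule can answer whether the arms differ in anxiety 6 weeks after surgery. It cannot answer whether the patient-centered video lowers anxiety before surgery, and a null at 6 weeks would leave that open.

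The schedule finding rests on the text of Section 11 and needs no assumption. The size of the loss does: it depends on how much of any early effect persists, about which the documents say nothing. If all of it persists, the 6-week reading loses little. If half or less persists, unadjusted power for an assumed 0.8 SD early effect falls to a third or below.

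The missing STAI row in Table 1 is a plain inconsistency with the text that cites it. Because the endpoint is exploratory, this is an inexpensive improvement and does not threaten the primary conclusion.

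**What to change.** 1. Section 11: add the six-item STAI to the questionnaires completed after video and counseling at the pre-operative visit.
2. Table 1: add a STAI row marked at baseline, after the video, and at 6 weeks.
3. Aim 4 and Section 7: state both time points. The post-video reading addresses anxiety before surgery; the 6-week reading stays as the later exploratory endpoint.
4. Section 12: specify a between-arm comparison of the STAI at each time, adjusted for the baseline STAI (for example, analysis of covariance). At present the only analysis that could cover it is the general statement about two-way ANOVA. Reconcile Sections 11 and 24 on when consent and baseline data are obtained, so that the adjusting STAI clearly precedes randomization.

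The cost is a protocol amendment and a minute or two more per patient at a visit where four questionnaires are already completed. No extra visit or staff is needed. The new reading falls on the day of randomization, so it should also escape most of the 20% loss to follow-up allowed for.

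If the investigators intend only the post-operative question, the minimum change is to write 6 weeks into Aim 4, correct Table 1, and state that the result does not bear on anxiety before surgery.
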